15.3 Risks Associated with Participation in this Clinical Investigation

As part of study participation, subjects will undergo a series of cMRI scans. As the CardioMEMS PA Sensor is non-ferrous and MRI conditional, there are no anticipated additional risks introduced to trial subjects due to cMRI. All risk mitigations associated with MRI use in conjunction with the CardioMEMS HF System are included in the Sensor Design FMEA (Reference: TR-1002-70, Rev. AA). Subjects will also be administered a study medication at each of the two study visits in order to modulate cardiac output. Possible protocol administered medication interactions are described below in section 15.4.

15.4 Possible Interactions with Protocol-Required Concomitant Medication

15.5 Steps Taken to Control or Mitigate Risks

Every possible effort will be taken to minimize, control, or mitigate risks associated with the clinical investigation, including:

- Careful selection of experienced Investigators for the clinical trial
- Early and adequate monitoring for each clinical trial site per the trial monitoring plan
- Conducting the clinical trial in accordance with the CIP, all applicable laws and regulations and any conditions of approval imposed by the appropriate IRB or applicable regulatory authorities where the clinical trial is performed
- Training of investigators and all relevant site personnel on cMRI imaging procedures
- Training of Investigators both on the CIP and the CardioMEMS HF System use in the study and in conjunction with MRI imaging
- Securing compliance of non-compliant sites (see Section 10.5)
- · Requiring medical supervision of study administered drugs by appropriate site personnel

The IFU also states that the devices can only be used by physicians who have received appropriate training on how to use the device. This statement is interpreted to mean that the physician users are

Template: 86357 Rev. J Page 39 of 61

expected to be aware of the known and foreseeable safety risks associated with the use of the devices including the surgical and/or non-surgical treatment of these conditions.

Risks associated with the use of the device under investigation are minimized through device design, investigator selection and training, pre-specified patient eligibility requirements, study monitoring to ensure adherence to the protocol. Sites will report all adverse events and device deficiencies to the Sponsor and the Sponsor will monitor internally for safety surveillance purposes.

15.6 Risk to Benefit Rationale

Congestive HF is a progressive disease and HF patients are generally symptomatic. Symptoms of dyspnea and fatigue increase with elevations of pressures within the heart and lungs, leading to instances of acute HF decompensation. The CardioMEMS HF System enables clinicians to medically manage HF patients by adjusting treatments to keep PA pressures within target ranges to prevent or reduce instances of acute HF decompensation. In doing so, the CHAMPION trial demonstrated a reduction in rates of HF decompensation resulting in an HFH, in NYHA Class III patients who had a HFH within the prior 12 months. In addition to pressure, CO is an important variable to describe hemodynamic pathophysiology in patients with HF. Deriving CO as part of remote monitoring with the CardioMEMS HF System is expected to produce an accurate assessment of CO without the associated risks and costs of traditional methods such as Fick and Thermodilution. CO monitoring using the CardioMEMS HF System can potentially provide important information to manage patients with HF. There are no new or additional risks related to the study device as part of the study protocol beyond the risks already incurred by the study subjects as they will already be implanted with the CardioMEMS PA Sensor and are currently using the CardioMEMS HF System. As part of study participation, subjects will undergo a series of cMRI scans. Since the CardioMEMS PA Sensor is non-ferrous and MRI conditional, there are no anticipated additional risks introduced to trial subjects due to cMRI. Subjects will also be administered a study medication to modulate CO. All precautions, including medical supervision during medication administration, will be taken to minimize any potential adverse effects from the medication administered per protocol. With the appropriate mitigations in place, the risks associated with participation in this study are outweighed by the potential benefit of providing CO via remote monitoring without the risks and costs associated with other CO assessments.

Template: 86357 Rev. J Page **40** of **61**

16.0 APPENDIX I: ABBREVIATIONS AND ACRONYMS

ADE Adverse Device Effect

ADHF Acutely Decompensated Heart Failure

AE Adverse Event
BMI Body Mass Index

BNP Brain Natriuretic Peptide

CHAMPION CardioMEMS™ HF Sensor Allows Monitoring of Pressures to Improve Outcomes

in NYHA Functional Class III HF Patients

CI Confidence Interval

CIP Clinical Investigation Plan

CRF Case Report Form CO Cardiac Output

CRT Cardiac Resynchronization Therapy

CRT-D Cardiac Resynchronization Therapy – Defibrillator CRT-P Cardiac Resynchronization Therapy – Pacemaker

DMP Data Management Plan

DSRC Device/System Related Complication

EDC Electronic Data Capture

EF Ejection Fraction

eGFR Glomerular Filtration Rate
FDA Food and Drug Administration
FMEA Failure Mode Effect Analysis

GCP Good Clinical Practice

GDMT Guideline Directed Medical Therapy

HA Hazard Analysis

HES Hospital Electronic System

HF Heart Failure

HFH Heart Failure Hospitalization

HFpEF Heart Failure with Preserved Ejection Fraction
HFrEF Heart Failure with Reduced Ejection Fraction

HR Heart Rate

ICMJE International Committee of Medical Journal Editors

IDE Investigational Device Exemption

IFU Instructions for Use

IRB Institutional Review Board

LVEF Left Ventricular Ejection Fraction
MEMS Micro-ElectroMechanical Systems

MEMS-HF CardioMEMS European Monitoring Study for Heart Failure

NT-proBNP N-Terminal pro-Brain Natriuretic Peptide

Template: 86357 Rev. J Page **41** of **61**

NYHA New York Heart Association

PA Pulmonary Artery
PAS Post-Approval Study

PCWP Pulmonary Catheter Wedge Pressure

PES Patient Electronics System
PMA Pre-Market Approval

RAP Risk Analysis Plan

RHC Right Heart Catheterization
SADE Serious Adverse Device Effect

SAE Serious Adverse Event SAP Statistical Analysis Plan

SV Stroke Volume

UADE Unanticipated Adverse Device Effect

VICTOR ValIdation of CardioMEMS HF SysTem Cardiac Output AlgoRithm IDE

Template: 86357 Rev. J Page **42** of **61**

17.0 APPENDIX II: DEFINITIONS

- NYHA HF Classification: The NYHA HF Classification provides a simple way of classifying the
 extent of HF. It places subjects in one of four categories, based on how much they are limited
 during physical activity:
 - Class I. Patients with HF, but without resulting limitations of physical activity. Ordinary physical activity does not cause undue fatigue, palpitation, or dyspnea.
 - Class II. Patients with HF resulting in slight limitation of physical activity. They are comfortable at rest. Ordinary physical activity results in fatigue, palpitation, or dyspnea.
 - Class III. Patients with HF resulting in marked limitation of physical activity. They are comfortable at rest. Less than ordinary physical activity causes fatigue, palpitation, or dyspnea.
 - Class IV. Patients with HF resulting in inability to carry on any physical activity without discomfort. Symptoms of cardiac insufficiency, anginal syndrome, and dyspnea may be present even at rest. If any physical activity is undertaken, shortness of breath is increased.
- Hospitalization: Admission to hospital for at least 24 hours.
- Adverse Event (AE): Any untoward medical occurrence, unintended disease or injury, or untoward clinical signs (including abnormal laboratory findings) in subjects, users, or other persons, whether or not related to the investigational medical device under clinical investigation. This definition includes events related to the investigational medical device or the comparator. This definition includes events related to the procedures involved.
- Serious AE (SAE): An AE that led to:
 - Death
 - A serious deterioration in the health of the subject, that either resulted in:
 - A life-threatening illness or injury OR
 - A permanent impairment to a body structure or a body function OR
 - An inpatient or prolonged hospitalization OR
 - A medical or surgical intervention to prevent life-threatening illness or injury or permanent impairment to a body structure or a body function OR
 - Fetal distress, fetal death or a congenital abnormality or birth defect

Note: A planned hospitalization for a pre-existing condition, or a procedure required by the CIP is not considered an SAE.

- Adverse Device Effect (ADE): An AE related to the use of an investigational medical device.
 This definition includes AEs resulting from insufficient or inadequate instructions for use,
 deployment, implantation, installation, or operation, or any malfunction of the investigational
 medical device. This definition includes any event resulting from the use error or from intentional
 misuse of the investigational medical device.
- **Serious Adverse Device Effect (SADE)**: ADE that has resulted in any of the consequences characteristic of a serious AE.
- Unanticipated Adverse Device Effect (UADE): As defined in 21 CFR §812.3, any serious adverse effect on health or safety or any life-threatening problem or death caused by, or associated with, a device, if that effect, problem, or death was not previously identified in nature,

Template: 86357 Rev. J Page **43** of **61**

severity, or degree of incidence in the CIP or application (including a supplementary plan or application), or any other unanticipated serious problem associated with a device that relates to the rights, safety, or welfare of subjects.

- Non-AE Device Issue: any instance when the device fails to perform or does not function properly without an associated an adverse clinical outcome.
- Device/System Related Complication (DSRC): An AE that is related or possible related to the system (CardioMEMS PA Sensor or other components of the CardioMEMS HF System) and has at least one of the following characteristics:
 - o is treated with invasive means (other than intramuscular medication or a right heart catheterization which is used for diagnostic purposes)
 - o resulted in the death of the subject
 - o resulted in the explant of the device

18.0 APPENDIX III BODY MASS INDEX CALCULATOR

Subjects' BMI will be calculated using the website below:

https://www.nhlbi.nih.gov/health/educational/lose wt/BMI/bmicalc.htm

Enter the subjects Weight and Height and then calculate BMI (print screen for source documentation)

Formulas used to calculate BMI:

English BMI Formula

BMI = Weight in pounds/ (height in inches x height in inches) x 703

Metric BMI Formula

BMI = Weight in kilograms/ (height in meters x height in meters)

Template: 86357 Rev. J Page **44** of **61**

[figure not shown]

19.0 APPENDIX IV: CARDIAC MRI PROTOCOL SPECIFIC IMAGE ACQUISITION OUTLINE

[figure not shown]

Template: 86357 Rev. J Page **45** of **61**

[figure not shown]

Any Protocol deviation must be documented in the "comments" section of the transmittal form.

Template: 86357 Rev. J Page **47** of **61**

Acquisition Planning Guide 19.6

19.6.1 Localizer/Scout (SSFP)

[figure not shown]

Template: 86357 Rev. J Page 49 of 61

[figure not shown]

Template: 86357 Rev. J Page 51 of 61

[figure not shown]
19.6.2

Validation of CardioMEMS HF System Cardiac Output Algorithm IDE Clinical Investigation Plan

Template: 86357 Rev. J Page 52 of 61

[figure not shown]

Template: 86357 Rev. J Page 53 of 61

21.0 APPENDIX VI: REVISION HISTORY

This CIP may be amended as appropriate by the Sponsor. Rationale will be included with each amended version in the revision history table below. The version number and date of amendments will be documented.

IRB and relevant Regulatory Authorities, if applicable, will be notified of amendments to the CIP.

Template: 86357 Rev. J Page 58 of 61

22.0 APPENDIX VII: CIP SUMMARY

| Clinical Investigation Name and Number | VICTOR IDE (|
|---|--|
| Title | V al l dation of C ardioMEMS HF Sys T em Cardiac O utput Algo R ithm IDE |
| Objectives | There are two primary objectives of this clinical investigation. The first objective is to finalize development of the algorithm estimating CO by collecting paired cMRI measurements of CO, as well as other parameters of heart function, and CardioMEMS HF System readings in the same subject. The second objective of this clinical investigation is to use data collected during the validation phase, distinct from the subjects within the development phase, to evaluate the agreement between the CardioMEMS HF System-derived CO and the CO values from cMRI in patients previously implanted with the commercially available CardioMEMS HF System. |
| Device Under Investigation | CardioMEMS HF System |
| Number of Subjects Required for Inclusion in Clinical Investigation | Up to 90 subjects will be enrolled |
| Clinical Investigation Design | This is a prospective, multi-center clinical study of patients previously implanted with the CardioMEMS PA Sensor. The clinical study will be conducted in up to 15 centers in the United States. |
| Primary Endpoint | The primary endpoint of this clinical investigation is to estimate CO from CardioMEMS HF System data. The estimated CO will be evaluated for agreement between the CardioMEMS HF System-derived CO and the CO values from cMRI in patients with the CardioMEMS HF System. |
| Subject Follow-up | Clinical sites will follow each subject until they complete their 3-month visit or withdraw from the study. Two in-person visits: Baseline and 3-month |
| Inclusion Criteria | Subject is willing and able to provide written informed consent prior to any clinical investigation-related procedure. |

Template: 86357 Rev. J Page 59 of 61

| | - |
|--------------------|---|
| Evaluaios Oritorio | Subject is implanted with the CardioMEMS PA Sensor for a minimum of 3 months at time of consent. Subject is ≥ 18 years of age. Subject is willing and able to undergo several cardiac MRI scans. This is including but not limited to: Subject must have all MRI compatible devices Subject must be able to hold their breath during imaging Subject must be free of all metal bodies, fragments, or implants that would prohibit MRI imaging Subject is willing and able to upload PA pressure information (i.e., take daily CardioMEMS HF System readings and have their hemodynamic information collected at study visits) and comply with the follow-up requirements. |
| Exclusion Criteria | Subject will receive or is likely to receive an advanced therapy (e.g., mechanical circulatory support or cardiac transplant) in the next 6 months. Subject was implanted with Cardiac Resynchronization Therapy (CRT)-Pacemaker (CRT-P) or CRT-Defibrillator (CRT-D) for less than 90 days prior to consent. Subject is pregnant or planning to become pregnant in the next 6 months Subject is enrolled into another trial with an active treatment arm Subject has significant congenital heart disease that has not been repaired Subject is implanted with mechanical right heart valve(s) Subject has unrepaired severe valvular disease Subject has an anticipated life expectancy of < 6 months Subject has an active, ongoing infection, defined as being febrile, an elevated white blood cell count, on intravenous antibiotics, and/or positive cultures (blood, sputum, or urine) Subject has and a major cardiovascular event (e.g., unstable angina, myocardial infarction, percutaneous coronary intervention, open heart surgery, or stroke, etc.) within 90 days prior to consent Subject has any condition that, in the opinion of the Investigator, would not allow for utilization of the CardioMEMS HF System to manage the subject using information gained from hemodynamic measurements to adjust medications, including the presence of unexpectedly severe pulmonary hypertension (e.g., trans-pulmonary gradient >15) at implant RHC, a history of non-compliance, or any condition that would preclude ability to obtain CardioMEMS PA Sensor readings and paired cardiac MRI data from being collected Subjects who, in the opinion of the investigator, are at-risk for serious adverse reaction to Dobutamine (ex. subjects with idiopathic hypertrophic subaortic stenosis and subjects who have shown previous |

| manifestations of hypersensitivity to Dobutamine) should be excluded |
|--|
| from the study |

1.0 SYNOPSIS OF STUDY DESIGN

[figure not shown]
1.1 Purpose of the Statistical Analysis Plan

This statistical analysis plan (SAP) is intended to provide a detailed and comprehensive description of the planned methodology and analysis to be used for Clinical Investigational Plan (CIP) the Validation of CardioMEMS HF System Cardiac Output Algorithm (VICTOR) IDE clinical investigation. This plan is based on Version B Clinical Investigation Plan.

1.2 Clinical Investigation Objectives

There are two primary objectives of this clinical investigation. The first objective is to finalize development of the algorithm estimating CO by collecting paired cardiac Magnetic Resonance Imaging (cMRI) measurements of CO, as well as other parameters of heart function, and CardioMEMS HF System readings in the same subject. The second objective of this clinical investigation is to use data collected during the validation phase, distinct from the subjects within the development phase, to evaluate the agreement between the CardioMEMS HF System-derived CO and the CO values from cMRI CO values in patients previously implanted with the commercially available CardioMEMS HF System.

[figure not shown]
1.3 Clinical Investigation Design

Statistical Analysis Plan

Figure 1: Clinical Investigation Design

During validation, measurement data from a distinct subject cohort to subjects included in the development phase will be used to determine if the chosen algorithm meets the validation criteria.

designed this clinical investigation to involve as little pain, discomfort, fear, and any other foreseeable risk as possible for subjects. Refer to the Risk Analysis in Section 15.0 of this clinical investigation plan for details.

Statistical Analysis Plan

1.4 Endpoints

1.4.1 Primary Endpoint and Rationale

The primary endpoint of this clinical investigation is to estimate CO from CardioMEMS HF System data. The estimated CO will be evaluated for agreement between the CardioMEMS HF System-derived CO and the CO values from cMRI in patients with the CardioMEMS HF System. Specifically, the primary endpoint will compare the two paired measurements taken at rest, collected during the 3-month follow-up visit from subjects allocated to the validation phase. Paired measurements will be compared using Deming regression. Agreement will be assessed through estimating the regression parameters of slope and intercept and evaluating their proximities to unity (slope=1 and intercept=0).

1.4.2 Descriptive Endpoints

Paired measurements will be evaluated for the following data samples:

- Baseline measurements recorded at rest
- Baseline measurements recorded following introduction of Dobutamine
- 3) All Baseline measurements
- 4) 3 Month measurements recorded at rest
- 5) 3 Month measurements recorded following introduction of Dobutamine
- All 3 Month measurements
- 7) Baseline and 3 Month measurements recorded at rest
- 8) Baseline and 3 Month measurements recorded following introduction of Dobutamine
- 9) All Baseline and 3 Month measurements

Each data sample will be analyzed using Deming regression methods described for the primary endpoint, Bland-Altman methods, and relative error will be computed using the method proposed by Shoemaker et al.⁴

1.5 Blinding

Investigators and subjects will not be blinded.

Statistical Analysis Plan

2.0 ANALYSIS CONSIDERATIONS

2.1 Analysis Populations

2.1.1 Enrolled Population

The Enrolled population includes all enrolled subjects (development phase and validation phase),

- Informed Consent obtained
- Inclusion/Exclusion criteria satisfied

2.1.2 Per Protocol (PP) Population

2.2 Statistical Methods

2.2.1 Descriptive Statistics for Continuous Variables

Continuous variables will be summarized with the numbers of observations, means and standard deviations, with quartiles, minimum and maximum.

[figure not shown]
2.2.2 Descriptive Statistics for Categorical Variables

Categorical variables will be summarized with subject counts and percentages/rates.

2.3 Endpoint Analysis

2.3.1 Primary Endpoint

[figure not shown]
The primary endpoint of this clinical investigation is to estimate CO from CardioMEMS HF System data. The estimated CO will be evaluated for agreement between the CardioMEMS-derived CO and the CO values from cMRI in patients with the CardioMEMS HF System. Specifically, the primary endpoint will compare the two paired measurements taken at rest, collected during the 3-month follow-up visit from subjects allocated to the validation phase.

86379 Ver. G Template

[figure not shown]
Statistical Analysis Plan

86379 Ver. G Template

Statistical Analysis Plan

2.5 Interim Analysis

No formal interim analyses are planned for this study. As such, no formal statistical rule for early termination of the trial is defined.

2.6 Timing of Analysis

2.7 Trial Success

The trial will be considered successful if Deming regression 95% confidence interval of the slope contains 1 and the 95% confidence interval of the intercept contains 0 for the primary endpoint.

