2.11 Multiplicity

This study includes a single primary endpoint. Thus, no Type I error adjustment is necessary.

Statistical Analysis Plan

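### Two separate interval checks on slope and intercept can often pass a device with a constant bias, because resting CO lies far from zero

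*SAP*

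**What the plan says.** SAP 2.7 (Trial Success) makes success depend on two conditions, both from the Deming fit: "95% confidence interval of the slope contains 1 and the 95% confidence interval of the intercept contains 0 for the primary endpoint". SAP 1.4.1 fixes the data: "the primary endpoint will compare the two paired measurements taken at rest, collected during the 3-month follow-up visit from subjects allocated to the validation phase". It describes agreement as closeness of the slope to 1 and of the intercept to 0.

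No joint region for the two parameters, limit on the mean difference or acceptance margin appears in the readable text. SAP 2.11 treats the rule as one endpoint: "This study includes a single primary endpoint. Thus, no Type I error adjustment is necessary".

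Mean bias is analysed elsewhere. SAP 1.4.2 lists nine data samples, including 3-month rest, and says: "Each data sample will be analyzed using Deming regression methods described for the primary endpoint, Bland-Altman methods" and a relative-error method will be applied. Both SAP 1.4.2 and SAP 3.5 class these as descriptive.

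The validation-phase n is not readable. The protocol summary (Appendix VII) gives only the total over both phases: "Up to 90 subjects will be enrolled".

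**The concern.** Agreement means that the fitted line is the identity line, which is a joint statement about slope and intercept. The intercept is the fitted device reading at CO = 0, where no subject lies. Its interval is therefore wide, and its error is tied to the slope error. The point (slope 1, intercept 0) can lie inside both separate intervals and still be far outside the joint 95% region.

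A constant offset is the case that suffers. It is estimated precisely at the centre of the data, but the rule looks for it only at zero. Systematic under- or over-reading is the first thing a method comparison should detect, and the protocol introduction says the study is intended to support US market approval of the CO feature. As written, the trial could be declared successful while its own Bland-Altman table shows a mean bias whose interval excludes zero.

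**Working it through.** **Inputs.** The rule, the 95% level and the use of resting 3-month pairs come from SAP 2.7 and 1.4.1. The plan shows no pass rate to reproduce, and the following are assumptions. Base case: true CO normal with mean m = 4.5 and SD s = 1.2 L/min; error SD e = 0.5 L/min for both methods; correct error ratio; one pair per subject; n = 45; true slope 1.

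**Correlation of slope and intercept errors**, approximately -m/√(m² + s²):
- Base case: -4.5/√(20.25 + 1.44) = -4.5/4.657 = -0.97.
- Range for means 4 to 5.5 and SDs 0.8 to 2.0: -4/√20 = -0.89 to -5.5/√30.89 = -0.99.

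**Hand check of the base case.**
- Mean difference: variance 2e²/n = 0.5/45 = 0.0111, SE 0.105.
- Slope (equal errors, true slope 1): variance (2s²e² + e⁴)/(n·s⁴) = (0.72 + 0.0625)/(45 × 2.0736) = 0.00839, SE 0.092.
- Intercept: variance 0.0111 + 4.5² × 0.00839 = 0.181, SE 0.425, about four times the SE of the mean difference.
- Half-width of the intercept interval: 2.017 × 0.425 = 0.86 L/min (simulation with jackknife SEs: about 0.88).
- Offset -0.5: the intercept check passes with probability about Φ((0.86 - 0.5)/0.425) = Φ(0.84) = 0.80.
- Offset -1.0: about Φ((0.86 - 1.0)/0.425) = Φ(-0.33) = 0.37.

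The slope check removes little more, because the true slope is 1. By contrast, -0.5 is 0.5/0.105 = 4.7 standard errors of the mean difference.

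**Simulation of the base case** (10,000 trials; jackknife SEs with t on n-2 df; joint F(2, n-2) region; paired t-test):

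| True offset (L/min) | SAP 2.7 rule passes | Joint 95% region accepts |
|---|---|---|
| 0 | 93% | about 94% |
| -0.5 | 79% | 1% |
| -1.0 | 36% | 0% |

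At -0.5, the paired mean difference is significant in 99.5% of the trials that pass.

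**By n, offset -0.5:** passes 89% (n = 20), 85% (30), 79% (45), 73% (60), 61% (90).

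**Cause isolated.** In a neighbouring case (mean 5, SD 1.2, error SD 0.5, n = 45, bias 0.5) the rule passes 78%. With CO centred at zero it passes 0.7%.

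**Grid of 192 settings** (mean 4 to 5.5; SD 0.8 to 2.0; n 30, 45, 60; cMRI/device error SD 0.35/0.35, 0.5/0.5, 0.3/0.6, 0.3/1.0):
- Offset -0.5 passes 7% to 92%, median 77%, and at least 50% in 164 of 192 settings.
- The joint region accepts that offset in a median of 0.8% of trials, maximum 40%.
- The mean-difference test detects it in 70% to 100%, median 99.8%.
- Offset -1.0 passes 0% to 89%, median 32%.

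**Variations at n = 45.**
- Two resting replicates averaged, independent errors (base case): offset -0.5 passes 62% and offset -1.0 about 8.5%. Over the grid, -0.5 passes 2% to 88%, median 56%.
- Error ratio wrongly fixed at 1, cMRI error 0.3: offset -0.5 passes 48% (device error 0.6) or 31% (device error 1.0), but an unbiased device then passes only 85% or 52%.

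**The case against.** **Assumed inputs.** Every percentage rests on values the documents do not show: validation n, CO distribution, error SDs, error ratio and replicate handling. With small errors and a wide CO spread, the rule does catch the offset. This stands as a limit on the size, which is why a range is given. It does not affect the mechanism.

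**Replicates.** The protocol contents list first and second at-rest acquisitions, and both reference lists include a paper on agreement with several observations per individual. Two resting readings per visit may therefore be the real design. In the base case a -1.0 offset is then usually caught, but the -0.5 offset still passes in well over half of trials.

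**Sample size.** Protocol 3.0 says subjects may be added to both cohorts, so a validation n below 90 is an inference from the stated cap on total enrolment. Even at n = 90 the -0.5 offset passes 61%.

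**Hidden text.** Parts of SAP 2.3.1, Appendix B and the protocol's success section cannot be read and may hold a further criterion. SAP 2.7, however, is a complete, readable definition of success and contains none.

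**Clinical importance.** A statistically clear 0.5 L/min is not necessarily important, and no readable margin settles that. This is correct, and it argues for stating a margin.

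**Already reported.** Bland-Altman results would be published with the verdict. That is true, but they cannot alter it.

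**Conclusion.** The concern holds. The success rule in SAP 2.7 is a weak check for constant bias because it tests the intercept at CO = 0 and ignores its near -1 correlation with the slope. Under the base assumptions a device reading 11% low in everyone passes about 79% of the time with single pairs and about 62% with two averaged replicates, against about 1% or less for a joint region. Over the single-pair grid the range is 7% to 92%. The mechanism follows from the rule and from resting CO being far from zero. How often it would matter in this trial depends on the unreadable inputs. It must be fixed because it affects the only success criterion. If a joint or mean-bias criterion exists in the hidden text, 2.7 should state it.

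**What to change.** Change SAP 2.7 in one of two ways.

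1. Replace the two checks with one test: the joint 95% confidence region for (slope, intercept) must contain (1, 0).
2. Keep the two checks and add a requirement on the fitted bias, intercept + (slope - 1) × CO, with its confidence interval at the validation-cohort mean CO. A Deming line passes through the two means, so at that point the fitted bias equals the mean paired difference, the Bland-Altman bias already planned.

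Preferably also require the fitted bias at stated low and high resting CO values to lie within a prespecified, justified margin. Centring CO alone covers only the mean.

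**Cost.** Either change needs SAP wording and a few lines of code on data already planned. In the base case, adding a requirement that the 95% interval of the mean difference contain 0 passes an unbiased device 89% of the time (93% now) and a -0.5 offset about 0.3%.

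**Downside.** A joint or mean-difference test is still a no-significant-difference rule. It penalises precision: at n = 45 a -0.2 L/min bias (4%) stays in the joint region 63% of the time with both error SDs 0.5, but 35% with 0.35. It also favours imprecision: with device error 1.0, cMRI error 0.3 and n = 30, the joint region accepts the -0.5 offset 41% of the time.

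A margin removes this fault but needs justification and possibly more subjects. With a purely illustrative 0.5 L/min margin at the mean and the 10th and 90th percentiles, an unbiased device at n = 45 passes 31% (error SD 0.5) or 84% (0.35).
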